EUS-FNA is now considered to be the usual method of sampling; however, the diagnostic yield is low: 38% to 82% [3-6]. Moreover, EUS-FNA often provides insufficient specimens which may not allow for immunohistochemistry that is often essential for diagnosis [7]. Thus EUS-CNB has been assessed for the purpose of obtaining a core sample which allows for histological assessment. Published data reveals a diagnostic (though not histologic) yield using EUS-CNB of 75% [7].

In 2011, the SINK technique for sampling was presented with a reported diagnostic accuracy of 92.8% [8]. The technique utilizes a conventional needle-knife connected to an electrosurgical unit. A 6 to 12-mm mucosal incision is made over the lesion. Then

conventional biopsy forceps are introduced to obtain 3-5 samples. Subsequently, the incision is closed with 2 to 3 endoclips.

The purpose of this study is to prospectively compare the efficacy and safety of EUS-CNB with SINK in patients with upper GI SETs. Our hypothesis is that the SINK technique will be superior to the EUS-CNB in obtaining a histological specimen. The results of the study would provide data which may improve the diagnostic ability for SETs. This in turn will guide appropriate surveillance or management (surgical or endoscopic) for patients with these lesions.

2. Objectives (include all primary and secondary objectives)

Primary Outcome Measures

To compare the diagnostic accuracy of the single-incision with needle knife (SINK) with the EUS-guided core needle biopsy (CNB)

Secondary Outcome Measures

1. To compare rates of diagnostic histological tissue acquisition
2. To compare the rates of technical failure between the 2 techniques
3. To compare the rate of adverse events between the 2 techniques
4. To compare the procedure time of EUS-CNB and SINK
5. To compare the diagnostic contribution of immunohistochemistry (when needed) between the 2 techniques

3. Background (briefly describe pre-clinical and clinical data, current experience with procedures, drug or device, and any other relevant information to justify the research)

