Thus, this study will provide essential data on two techniques to help decipher which is the optimal method of tissue acquisition.

We hypothesize that the SINK technique will have a higher diagnostic accuracy than EUS-CNB for the diagnosis of UGI SETs.

4. Study Procedures

- Study design, including the sequence and timing of study procedures (distinguish research procedures from those that are part of routine care).

This is a prospective, randomized study. All procedures are part of routine care and not experimental. All patients will begin their endoscopy with a standard gastroscope followed by electronic radial/linear scanning video echoendoscope prior to randomization to ascertain the wall layer of origin for the tumor. This EUS exam will be performed under the same anesthetic as the study intervention. Patients will be consented prior to endoscopy.

Patients who are candidates for this study (see inclusion criteria) will be randomized as to receive either EUS-CNB or SINK technique (computer generated randomization sequence, sealed envelopes). The endoscopist will not be blinded to the type of technique used however the study pathologist will be blinded.

Patients receiving the EUS-CNB technique:

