slipping of the knife off the lesion. The incision should be deep enough such that it penetrates the mucosa and submucosa. A conventional biopsy forceps (Radial Jaw4, Boston Scientific, Natick, Mass) is then deeply introduced through the hole, and 2 bites are obtained per pass. A total of 4 passes will be performed, by passing the biopsy forceps through the incision on each occasion. The mucosal incision will then be closed with endoclips whenever possible. If the endoscopist at the time is concerned about inadequate tissue acquisition and plans to perform a subsequent intervention (i.e. EUS-CNB, EUS-FNA) then the endoclips will be placed after the EUS. Biopsies will be placed in formalin bottles and sent for histopathology. In case of technical failure, the endoscopist is permitted to choose another method to obtain biopsies (e.g. EUS-CNB, EUS-FNA...)

Pathologic evaluation

Specimens will be placed in buffered formalin and processed as normal forceps biopsy specimens; however, special care will be taken not to lose tiny specimen fragments. The pathologists will be blinded to the type of technique used, but all other information about the clinical history and site biopsied will be given. A positive diagnosis of a specific malignancy or of a specific benign disease by either technique will be accepted as a true positive. A histological diagnosis of atypical cells or abnormal cells will be considered a negative result. For malignancy, an “accurate diagnosis” will be considered one in which a tissue diagnosis obtained is compatible with that seen by subsequent surgery, alternative biopsy by another needle or sites, or clinical follow up.

Final diagnosis and definition

In the absence of surgical resection, diagnostic histology obtained by either technique will be considered the gold standard. When diagnostic histology is not available, a definitive diagnosis is established on the basis of long-term follow-up, surgery, or further procedures with biopsy. The diagnostic accuracy will be defined as the ratio between the sum of true positive and true negative values divided by the total number of procedures done in either technique. As per the discretion of the pathologist, the specimens may be subjected to immunostaining and if performed, the contribution to the diagnostic yield will be noted.

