With the assumption that diagnostic yield of “EUS-CNB” is 70% and that of “SINK” is 95%, and considering $\alpha = 5\%$ and $1-\beta = 80\%$, the required sample size is 36 patients in each group (total of 72 patients).

We will account for 20% drop out rate, giving a total of 90 patients, 45 in each arm.

Statistical analyses

Categorical parameters including gender, location of lesion, technical success and diagnostic accuracy will be compared by χ^2 -test or Fisher’s exact test. To compare diagnostic accuracy between the two techniques, we will use McNemar’s test. Continuous variables including age, size of lesion, follow-up period, needle passes and adequacy of specimens will be compared by the Student’s *t*-test or Wilcoxon rank sum test. All statistical analyses will be performed using SPSS software (version 15.0; SPSS, Chicago, IL), with results considered significant at *P* values < 0.05 .

- d. Early stopping rules.

A data safety and monitoring board (DSMB) will be appointed comprised of interventional endoscopists, mainly of [name], [name], and [name]. The DSMB will be responsible for reviewing all major complications (perforation, hospitalization for > 48 hours, bleeding requiring transfusion, deaths etc). If any serious adverse event is noted during the study then the DSMB will be required to meet. Additionally. The DSMB will perform a blinded analysis after enrolment and initial outpatient follow-up of 50% of the study cohort.

Interim analysis will be performed at 50% recruitment. If a $> 20\%$ difference in sensitivity is found between both methods then the study will be terminated early.

8. Risks

- a. Medical risks, listing all procedures, their major and minor risks and expected frequency.

This study is classified as greater than minimal risk and potential complications related to EUS-CNB or SINK procedure are following:

- 1) The needle puncture may cause inflammation or scarring of the lining of the digestive tract which may cause abdominal pain and ulceration.
- 2) Perforation: Only physicians specially trained in EUS will be performing these procedures. Patients will be kept a minimum of 2 hours after the procedure is completed, during which time any perforation would be clinically recognized.

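### The primary comparison is assigned to McNemar's paired test, but patients are randomised to two independent arms

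*Combined protocol and SAP*

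**What the plan says.** - **Design (section 4, study design).** Eligible patients "will be randomized as to receive either EUS-CNB or SINK technique". Section 7c plans 45 in each arm. No matching is described, and nothing plans both techniques in every patient.
- **Endpoint (section 4, final diagnosis and definition).** Accuracy is true positives plus true negatives, "divided by the total number of procedures done in either technique". Comparing accuracy between SINK and EUS-CNB is the primary objective in section 2.
- **Tests (section 7c, statistical analyses).** Two consecutive sentences cover this endpoint. The first reads "Categorical parameters including gender, location of lesion, technical success and diagnostic accuracy will be compared by" the chi-square or Fisher's exact test. The second reads "To compare diagnostic accuracy between the two techniques, we will use McNemar"'s test.
- **Sample size (section 7c).** With 70% for EUS-CNB, 95% for SINK, alpha 5% and power 80%, the plan gives 36 per group. This becomes 90 in total after a 20% drop-out allowance. Sidedness is not stated.
- **Second techniques (sections 4 and 4e).** Another method is optional. It follows technical failure or a sample judged inadequate, and it may be EUS-FNA rather than the other study technique.

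**The concern.** McNemar's test uses only discordant pairs: patients in whom one technique was accurate and the other was not. In a parallel-group trial each patient supplies one outcome under one technique, so there is no such cross-classification. The only patients with results from both techniques would be discretionary cross-overs, chosen because the first technique appeared to have failed. They cannot estimate the randomised contrast.

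The sentence naming McNemar's test is the one written specifically for the between-technique comparison, so it reads as the governing one. If it is followed, the primary p-value is not computable, or depends on an arbitrary pairing of unrelated patients, or tests a different hypothesis. If it is ignored, the analyst departs from the written plan on the primary endpoint and may choose the test after seeing the data.

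**Working it through.** **1. Reproduce the planned sample size.** Inputs from section 7c: p1 = 0.95, p2 = 0.70, alpha 5% (two-sided assumed), power 80%. The mean proportion is 0.825. For two independent proportions with pooled variance under the null:

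n = [1.960 × √(2 × 0.825 × 0.175) + 0.8416 × √(0.95 × 0.05 + 0.70 × 0.30)]² / 0.25²

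= [1.0532 + 0.4271]² / 0.0625 = 35.06, so 36 per arm. Then 72 / 0.8 = 90. Both figures match the plan. A one-sided, continuity-corrected version also gives 36, so the sidedness remains an assumption, but that version too is for independent groups.

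**2. What a paired design would have needed.** With discordance πd and difference δ = 0.25:

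n = [1.960 × √πd + 0.8416 × √(πd − δ²)]² / δ²

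The margins 95% and 70% allow πd from 0.25 to 0.35.

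| πd | Pairs needed |
|---|---|
| 0.25 (minimum) | 29 |
| 0.95 × 0.30 + 0.05 × 0.70 = 0.32 (outcomes independent) | 38 |
| 0.35 (maximum) | 42 |

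The plan assumes no discordance rate, so the sample size was not built for McNemar's test.

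**3. Three ways the McNemar sentence could be carried out.**

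*(a) Technique-by-outcome table entered into the test (a hypothetical misuse).* The off-diagonal cells are then SINK failures and EUS-CNB successes. The test asks whether the two accuracies add up to 1, not whether they are equal. With both accuracies at 70% and 36 per arm, the expected counts are 36 × 0.30 = 10.8 and 36 × 0.70 = 25.2, although there is no difference. Exact enumeration over two Binomial(36, p) arms gives these rejection rates:

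| True accuracy in both arms | Rejection rate |
|---|---|
| 70% | 67.1% |
| 75% | 91.9% |
| 82.5% | 99.9% |

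*(b) Unrelated patients paired arbitrarily.* Take 33/36 for SINK and 26/36 for EUS-CNB, that is 3 and 10 failures. With k double-failure pairs the discordant counts are 10 − k and 3 − k:

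| k | Discordant counts | Exact McNemar p |
|---|---|---|
| 0 | 10, 3 | 0.092 |
| 1 | 9, 2 | 0.065 |
| 2 | 8, 1 | 0.039 |
| 3 | 7, 0 | 0.016 |

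The same 72 outcomes fall on either side of 0.05. An independent-groups test gives one answer. The pooled proportion is 59/72 = 0.819, and z = 0.1944 / √(0.8194 × 0.1806 × 2/36) = 2.14, so the uncorrected chi-square p is 0.032. Fisher's exact test on these data gives 0.063.

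*(c) Cross-over patients only.* Every pair is selected on apparent failure of the first technique, so the comparison favours whichever technique came second.

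**4. Power with an independent-groups test (exact, 95% versus 70%).**

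| Test | 36 per arm | 45 per arm |
|---|---|---|
| Chi-square, uncorrected | 85.1% | 92.4% |
| Fisher's exact | 75.9% | 86.3% |

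Using chi-square, and switching to Fisher when an expected count is below 5, gives 82% at 36 per arm.

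**The case against.** The strongest reply is that a valid test is already in the plan: the preceding sentence assigns accuracy to chi-square or Fisher, and the sample size agrees with it. On that view the McNemar sentence is a slip that a competent analyst would pass over. It is true that a valid test is named. But nothing gives it precedence, and the more specific sentence points to the invalid one.

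Other points on size are fair:

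- Case (a) is a misuse that the plan does not describe. It shows what could happen and is not a forecast.
- In case (b), pairing done blind to outcome does not inflate false positives. Exact McNemar then rejects about 2.8% of the time (both arms 70%) or 2.3% (both 82.5%), with about 74% power at the planned rates. In the example, p = 0.016 arises in only 1.7% of random pairings, and 82% give 0.065 or 0.092. The objection to this route is arbitrariness and lost power.
- In case (c), same-session cross-over rests on the endoscopist's impression or on technical failure. Some first specimens may later prove diagnostic, so these pairs are selected but need not all be failures on the endpoint.
- The choice left open between chi-square and Fisher also crosses 0.05 in the example (0.032 against 0.063). Deleting McNemar alone is therefore not enough.

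**Conclusion.** The concern holds. The test written for the primary comparison does not apply to this design, and it conflicts with a valid test named one sentence earlier. The conclusion rests only on the parallel allocation in section 4 and the wording of section 7c. The size depends on how the sentence would be carried out: a p-value set by arbitrary pairing (0.016 to 0.092 in the example), or, under the misuse in (a), false-positive rates of 67% to 99.9%. The planned 36 per arm already fits an independent-groups analysis, assuming a two-sided 5% level. This must be fixed because it concerns the primary endpoint.

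**What to change.** 1. Delete the McNemar sentence in section 7c.
2. Name one primary test: Pearson chi-square without continuity correction, comparing the randomised arms, with Fisher's exact test only if an expected count is below 5. At the planned rates and 36 per arm the switch would occur in about 15% of trials.
3. State the sidedness; a two-sided 5% level reproduces 36 per arm.
4. Report the difference in accuracy with a 95% confidence interval.
5. Bring the accuracy denominator in section 4 into line. It counts procedures, so a cross-over patient could enter both proportions and break independence. Each randomised patient should count once, in the assigned arm, on the assigned technique's result.

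The cost is essentially one sentence in section 7c, plus a clarifying phrase in the endpoint definition. No new data or extra patients are needed, and 90 in total stands.

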The study will be continued until the sample size of 90 patients is reached (estimated 2 years). The patients will only need to attend for the procedure as scheduled. No further visits are required.

b. Blinding, including justification for blinding or not blinding the trial, if applicable.

Blinding of the endoscopist is not practical as the endoscopist will be performing the technique. However, the pathologist will be blinded to the technique used.

c. Justification of why participants will not receive routine care or will have current therapy stopped.

Not applicable. This study compares two techniques which are considered standard of care for the diagnosis of these tumors. These procedures are not experimental.

d. Justification for inclusion of a placebo or non-treatment group.

This is not applicable to this study. All patients are presenting for a procedure they require for diagnosis as determined by their referring physician.

e. Definition of treatment failure or participant removal criteria.

In case of failure of the initial method to obtain adequate sample, another method may be performed at the discretion of the endoscopists. An inadequate sample is defined as samples of insufficient quality such that a histological diagnosis would not likely be obtained. This will be determined at the time of tissue acquisition if the samples obtained are only tiny fragments, no visible core tissue (i.e no worms) or it appears that only blood clot is present. Post procedure, an inadequate sample will be determined based on an inconclusive formal pathology report. In these cases, the patients may cross over to EUS-CNB or SINK (depending on their initial randomization) or undergo an EUS-FNA either at the time of the procedure (if it appears that no tissue has been obtained) or the patient will return at a later date for an EUS-CNB, SINK, EUS-FNA/be referred to surgery/undergo surveillance at 6-12 months etc, depending on the differential diagnosis.

f. Description of what happens to participants receiving therapy when study ends or if a participant's participation in the study ends prematurely.

This is not applicable in this study. The patient only attends for their diagnostic procedure; there is no further follow-up or treatment necessary as part of the study protocol.

5. Inclusion/Exclusion Criteria

Inclusion criteria:

1. Patients referred for EUS evaluation of upper GI SETs measuring an estimated 15mm or greater in maximal diameter.

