2. Location of SET: esophagus, stomach, duodenum
3. Age >18 years and older
4. Patient consent obtained

Exclusion Criteria:

1. Endoscopically non bulging lesion
2. Upper GI SETs <15mm in size as measured during study EUS
3. Lesions not necessitating tissue acquisition: i.e. lipomas, varices
4. Cystic lesion
5. Patients < 18 years of age
6. Uncorrectable Coagulopathy (INR >1,5, platelets <100,000)
7. Patients with stigmata of portal hypertension
8. Patients with post-surgical UGI anatomy (Roux-en-Y gastric bypass, esophagectomy etc)
9. Uncooperative patients
10. Pregnant women (women of childbearing age will undergo urine pregnancy testing, which is routine for all endoscopic procedures)
11. Refusal to consent form

Drop-outs (anyone will be considered a drop-out after randomization had been made):

1. Mass<15mm
2. Cystic
3. Lipoma
4. Varices

6. Drugs/ Substances/ Devices

- a. The rationale for choosing the drug and dose or for choosing the device to be used.

The 25 G needle is too small to be used for histological sampling, and the 19 G needle is too rigid impeding the sampling from the duodenum or the fundus of the stomach. The 22G Procore needle is readily available and clinically used for tissue sampling.

The needle knife sphincterotome and pinch biopsy forceps are readily available and used clinically for controlled mucosal incision and tissue sampling allowing, respectively.

Although used clinically, neither of these techniques has been compared at our institution.

- b. Justification and safety information if FDA approved drugs will be administered for non-FDA approved indications or if doses or routes of administration or participant populations are changed.

Not applicable

- c. Justification and safety information if non-FDA approved drugs without an IND will be administered.

Not applicable

7. **Study Statistics**

- a. Primary outcome variable.

We hypothesize that the diagnostic accuracy of single incision using needle knife (SINK) technique will “be superior” in obtaining histological samples than EUS-CNB.

Based on the previously published references that demonstrated the diagnostic accuracy of SINK is 92.8%⁸ and that of EUS-CNB is 70% [12], we assume that the diagnostic accuracy of SINK and EUS-CNB to be 95% and 70% respectively

- b. Secondary outcome variables.
 - Not applicable
- c. Statistical plan including sample size justification and interim analysis

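### The 50% interim rule stops the trial on a raw difference above 20%, below the 25-point design effect and with no alpha-controlled boundary, so 5% error and 80% power are not assured together

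*Combined protocol and SAP*

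**What the plan says.** - **Interim rule (section 7d).** "Interim analysis will be performed at 50% recruitment". If a more than 20% "difference in sensitivity is found between both methods then the study will be terminated early". The wording is mandatory. It does not say whether 20% is absolute or relative, or whether a stop is itself a positive result.
- **DSMB look (section 7d).** "The DSMB will perform a blinded analysis after enrolment and initial outpatient follow-up of 50% of the study cohort".
- **Sample size (sections 7a and 7c).** "we assume that the diagnostic accuracy of SINK and EUS-CNB to be 95% and 70% respectively". With alpha 5% and power 80%, "the required sample size is 36 patients in each group (total of 72 patients"), raised to 90 (45 per arm) for 20% drop-out.
- **Testing (section 7c).** Results are significant at P < 0.05, with no adjustment for the interim look. Diagnostic accuracy is assigned to chi-square or Fisher's exact test and, in the next sentence, to McNemar's test.
- **Primary objective (section 2).** "To compare the diagnostic accuracy of the single-incision with needle knife (SINK) with the EUS-guided core needle biopsy (CNB"). The interim rule names sensitivity instead.
- **Recruitment (section 4).** "The study will be continued until the sample size of 90 patients is reached (estimated 2 years").

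**The concern.** A stopping rule for a difference between arms needs a boundary that accounts for testing twice. This one is a raw point estimate. At half size a 20-point difference is well within chance, so the rule can stop a trial of two equally good techniques. Because the trigger is below the assumed effect, it is also the likely outcome when the sponsor's hypothesis is true. The trial would then end with half the data, an overestimated difference and sometimes a non-significant test. The sample size was calculated for a single look, so its error rate and power do not carry over to a trial run under this rule.

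**Working it through.** **1. The plan's own figure.** Two-sided alpha 5%, power 80%, rates 0.95 and 0.70, mean rate 0.825:

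n = [1.96·√(2·0.825·0.175) + 0.842·√(0.95·0.05 + 0.70·0.30)]² / 0.25² = 35.06, rounded up to 36 per arm.

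72 / (1 − 0.20) = 90. The stated figures reproduce, as a single-look design.

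**2. Assumptions for the interim rule.** 20% means percentage points; either direction counts; the rates for sensitivity equal those for accuracy; the arms are independent. Section 7d does not fix the numbers at the look, so two cases are shown: 18 vs 18 then 36 per arm (full drop-out), and 22 vs 23, either way round, then 45 per arm (no drop-out). All probabilities sum exact binomial probabilities over both stages. The trial stops if |a/n₁ − b/n₂| > 0.20; otherwise the final test is at 0.05.

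**3. What the trigger means at 18 per arm.** 0.20 × 18 = 3.6, so a difference of 4 patients stops the trial. For 17/18 vs 13/18 the pooled rate is 30/36 = 0.833 and z = 0.222 / √(0.833·0.167·2/18) = 1.79. Chi-square p is 0.074 and Fisher p is 0.18. The trial must stop on this result.

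**4. How often it stops.**

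| | 18/18 | 23 SINK/22 CNB | 22 SINK/23 CNB |
|---|---|---|---|
| Stops under 95% vs 70% | 67.6% | 65.2% | 70.2% |
| Mean observed difference at a stop (true 25 points) | 31.4 | 31.1 | 30.3 |
| Of these stops, chi-square p ≥ 0.05 | 21% | 8% | 8% |
| Of these stops, Fisher p ≥ 0.05 | 44% | 8% | 22% |
| Stops with no true difference, both rates 70% | 20.1% | 14.4% | 14.4% |
| both 82.5% | 12.2% | 7.6% | 7.6% |
| both 90% | 5.0% | 2.6% | 2.6% |
| both 95% | 1.0% | 0.3% | 0.3% |

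**5. Error and power by what a stop means.** Power is under 95% vs 70%; type I error is at a common rate in both arms.

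| Reading | 36 per arm | 45 per arm |
|---|---|---|
| A. A stop counts as success (chi-square at the final look) | Error 15-22% at 70-82.5%, 9% at 90%, 4% at 95%; power 88% | Error 11-17% at 70-82.5%, 7% at 90%, 5% at 95%; power 93-94% |
| B. Chi-square P < 0.05 also required | Error 6.4-7.7% at 70-90% (4.9-5.8% without the rule), 4.2% at 95%; power 74% (85% without) | Error 7.2-7.8% at 70-90%, 5.1% at 95%; power 88% (92% without) |
| C. Fisher P < 0.05 also required | Error at most 2.9%; power 53% (76% without) | Error at most 4.7%; power 74% (22/23) or 84% (23/22) (86% without) |

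**6. Other wordings.** If 20% is relative to the smaller rate, stops under 95% vs 70% rise to 78-83%, and chi-square power (reading B) is 66% at 36 per arm or 78-79% at 45. Relative to the larger rate, stops are 68-71% and power is 74% at 36 per arm, or 83% (23/22) or 87% (22/23) at 45. If only SINK-better differences count, stops under 95% vs 70% are unchanged and null stops roughly halve.

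**The case against.** - **The fixed design is not exact either.** At 36 per arm with no interim look, chi-square error already reaches 5.8% and Fisher power is 76%. This stands. The rule should be charged only with the increment, which is why step 5 gives the figures without it. The increment is still 11 power points (chi-square) or 23 (Fisher) at 36 per arm, and about 2 points of chi-square error.
- **The plan never says that a stop is a positive result.** This stands. The 11-22% error belongs to reading A only, and readings B and C sit better with the general P < 0.05 rule. Each still has a cost.
- **36 per arm is the full drop-out case.** The pre-randomisation EUS should remove many of the listed drop-out reasons. Nearer 45 per arm, chi-square power stays at 88%, and with Fisher and a 23 SINK/22 CNB split both properties hold. This also stands, but a plan cannot rely on no drop-out, a favourable split and a test it has not chosen.
- **The apparent conflicts are mild.** A two-directional difference can be checked on coded arms, so a blinded look is possible, though section 7d does not say so. The target of 90 is an ordinary recruitment statement to which a stopping rule is an exception. Sensitivity and accuracy nearly coincide here: every included patient has a lesion, and "A positive diagnosis of a specific malignancy or of a specific benign disease by either technique will be accepted as a true positive". These are wording points and the conclusion does not rest on them.
- **A 0.003 boundary is close to having no efficacy stop.** True under the assumed effect. Removing the stop is an equally sound choice.

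**Conclusion.** The concern holds. As written, section 7d requires a stop on an uncontrolled point estimate set below the design effect. Under the sponsor's own 95% vs 70%, about two-thirds of trials (65-70%) would end at half size with the difference overestimated by 5-6 points on average. The two design properties do not both fail on every reading. Error fails if a stop is success. If chi-square significance is required, error fails and, at 36 per arm, power does too. If Fisher significance is required, power fails, except at 45 per arm with 23 SINK/22 CNB. The error inflation fades as the common rate approaches 95%. These figures rest on the absolute-points reading and the other assumptions in step 2. The absence of a boundary and the trigger's position below 25 points are plain from the text. This should be corrected before the interim analysis is run.

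**What to change.** Replace the rule in section 7d with wording such as: *An unblinded statistician reporting only to the DSMB will compare diagnostic accuracy between arms once, at 50% information. The trial may stop for efficacy only if the two-sided chi-square p is at most 0.003 (Lan-DeMets spending, O'Brien-Fleming type). Otherwise the final analysis uses the same test at 0.049. Investigators do not see results by arm.* The classical O'Brien-Fleming pair (0.0052, then 0.048) is an alternative. Name one independent-groups test for both looks; McNemar's test needs paired data, which two randomised arms do not supply.

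With 0.003/0.049 and chi-square, power is 85% at 36 per arm and 92% at 45. Error at 36 per arm is at most 5.8% for common rates of 70-95%, the same maximum as the fixed test, and exceeds it by no more than about 0.0004 at any single rate. Counts at the interim are small (18 × 0.175, about 3 expected failures per arm), so Fisher is a reasonable choice. With Fisher, error is at most 2.9% and power is 76% at 36 per arm or 85% at 45.

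The simpler alternative is to delete the efficacy stop and keep the 50% look for safety only.

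Either way, change sensitivity to diagnostic accuracy, say how the blinded DSMB analysis relates to the interim comparison, and make the section 4 recruitment sentence subject to any stopping rule.

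Cost: protocol wording only, with N still 90. Under the assumed effect, early efficacy stopping (chi-square) falls from 65-70% to 8% (18/18) or 14-17% (22/23) with 0.003, or to 14% or 23-24% with 0.0052.
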